This is a Phase IV, multi-center, prospective, randomized controlled, comparator clinical trial. Twelve to fourteen (12-14) Level I Trauma Centers throughout the United States will participate as research sites conducting this protocol. After the research site receives Institutional Review Board (IRB) approval, patients between the ages of 18-70 years old who undergo open abdominal laparotomy for abdominal trauma or acute surgical abdomen within thirty-six (36) hours of initial presentation to their healthcare organization may be eligible for study inclusion. Exclusion criteria includes: known allergy to chlorhexidine gluconate (CHG), Abbreviated Injury Scale (AIS) score of six (6), American Society of Anesthesiologists Physical Status Classification (ASA) score of five (5) or greater, female subjects who are pregnant and/or breast feeding, those patients undergoing a damage control laparotomy, a drain is placed within the wound or an intra-abdominal drain exits through the primary incision, reoperation occurs through the primary incision or transgresses the primary incision as the index procedure within 30 days, and those enrolled in a concurrent, ongoing interventional, randomized clinical trial.

Patient risk factors will be assessed at screening include chronic uncontrolled hypertension, chronic heart disease, chronic renal disease, chronic pulmonary disease, diabetes mellitus, HIV, chronic liver disease, a BMI of less than 18 or above 40, coagulopathy, current long-term steroid use, current smoker, and current cancer. Additional assessments include PATI (Penetrating Abdominal Trauma Index), AIS and ASA scores, and adherence to SCIP prophylactic antibiotic-specific guidelines. Other measures to be documented will include antibiotic used and surgical skin preparation used. The following present on admission (PoA) characteristics are documented: shock, (systolic BP < 90 mm Hg), intubation, active infection, transfusion of blood/blood products and primary injury in trauma or primary organ(s) in the acute abdomen. Intra-operative SSI risk factors including drains, staple versus sutures, surgical time (skin to skin), blood/blood products, and body temperature below 36°C are assessed and risk adjusted in the final analysis.

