It is anticipated that treatment groups will be well balanced with respect to baseline and demographic characteristics as well as risk factors for SSI, however if there are imbalances these will be accounted for in a supportive analysis using logistic regression. In these analyses, a logistic regression model with treatment as a fixed categorical variable and key baseline/demographic variables that are imbalanced will be included in the model to obtain adjusted estimates of the treatment effect in the form of odds ratios with two-sided 95% confidence intervals. Identification of variables to include will be based on comparisons between the two groups using appropriate two-sided tests based on the underlying distribution of the data. Those variables that are found to be significant (p < 0.05) will be included in the model.

Secondary Endpoints

The rate of readmission within 30 days from the date of the abdominal surgical procedure will be analyzed using the same methods as described for the primary endpoint.

The length of stay in the hospital will be calculated as the difference between the date of discharge and the date of admission, plus 1 day. Length of stay will be summarized by treatment group using descriptive statistics. As length of stay data tends to be highly skewed, a comparison of the LOS between the two treatment groups will be made by modeling the log LOS using a mixed effect model with a fixed effect term for treatment and a random component for center. This means and 95% confidence intervals for the difference between treatment groups will be back transformed and presented along with the two-sided p-value from a two-sample t-test.

An additional analysis will seek to define risk-adjusted length of stay outliers and whether there are observed differences between the two study populations. Using the post-operative length of stay as the dependent variable, a linear model will be used by employing those patients in the study who had no complications identified through the entire 30 day postoperative period. Again, hospital variables will be used. The observed length of stay for all patients will then be compared to the expected length of stay from the model to determine

Study Number IRR-CT-901-2013-01	Version: 1.0	01AUG2014
© Confidential IrriMax Corporation		Page 29 of 35

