group using the MedDRA level hierarchy (system organ class, high level group term, high level term, and preferred term) as follows:

- Overall (i.e., regardless of severity or relationship to treatment)
- By severity grade (mild, moderate, severe, or life threatening)
- By relationship to study product (potential relationship to study product or unlikely/no relationship to study product) according to the mapping scheme below:
 - o Potentially related: will include all AEs with a relationship rating of "definite", "probably" or "possibly."
 - Unlikely/not related: will include all AEs with a relationship rating of "unlikely" or "unrelated."

Unless otherwise specified, at each level of patient summarization in reporting the incidence of the AEs, a subject will be counted once if the subject reported one or more events. If more than one occurrence of an event is reported, the event of the worst severity or the worst-case relationship assessment will be summarized.

AEs leading to premature discontinuation and serious AEs (SAEs) will also be summarized by treatment group and relationship. AEs leading to premature discontinuation will be defined as any AE with an action taken equal to "permanently discontinued."

Demographics and Baseline Summaries

Demographic variables (e.g., age, gender, race, ethnicity) and baseline characteristics (e.g., medical history, PATI, AIS and ASA scores, adherence to SCIP prophylactic antibiotic-specific guidelines, surgical skin preparation used, shock, (systolic BP < 90 mm Hg), intubation, active infection, transfusion of blood/blood products, primary injury in trauma or primary organ(s) in the acute abdomen and intraoperative risk factors), will be summarized by treatment group. The comparability of the treatment groups for relevant demographic and baseline characteristics will be assessed by descriptive statistics. No statistical hypothesis tests will be performed. For continuous data, summaries will include the number of observations, mean, standard deviation, median, 25th and 75th quartiles, minimum and maximum values. For categorical data, frequency counts and percentages will be reported.

Concomitant Medications/Antibiotics

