APPENDIX I: Study Specific Instructions for Use (IFU)

TO BE RETAINED BY CIRCULATOR

Protocol: IRR-CT-901-2013-01 STUDY SPECIFIC INSTRUCTIONS FOR USE (IFU):

- 1. Twist off seal caps from IrriSept® Step 1 and IrriRinse® Step 2 bottles.
- 2. Remove IrriProbe® applicators from tray and attach to bottles.
- 3. **After initial incision and dissection to the fascia, and before opening the fascia,** suction the surgical wound bed thoroughly to prevent dilution of IrriSept.
- 4. Invert IrriSept Step 1, direct fluid into wound, squeezing firmly with both hands, ensuring coverage of all areas of the wound bed and filling the wound space.
- 5. Allow solution to dwell for one (1) minute.
- 6. Suction residual fluid from the wound bed.
- 7. Invert IrriRinse Step 2, direct fluid into wound, squeezing firmly with both hands, ensuring coverage of all areas of the wound bed and filling the wound space.
- 8. Suction residual fluid from the wound bed.
- 9. At completion of Step 1 and Step 2, discard used bottles and applicators.
- 10. Use normal saline irrigation for all work below the level of the fascia.
- 11. **Prior to final closure repeat previous steps with second kit (unit carton)** by twisting off seal caps from IrriSept Step 1 and IrriRinse Step 2 bottles.
- 12. Remove IrriProbe applicators from tray and attach to bottles.
- 13. **After fascia closure,** suction the surgical wound bed thoroughly to prevent dilution of IrriSept.
- 14. Invert IrriSept Step 1, squeeze firmly with both hands, direct fluid into wound, ensuring coverage of all areas of the wound bed and filling the wound space.
- 15. Allow solution to dwell for one (1) minute.
- 16. Suction residual fluid from the wound bed.
- 17. Invert IrriRinse Step 2, squeeze firmly with both hands, direct fluid into wound, ensuring coverage of all areas of the wound bed and filling the wound space.
- 18. Suction residual fluid from the wound bed.
- 19. At completion of irrigation, discard used bottles and applicators.

FOR STUDY USE ONLY IFU-901-REV01

Study Number IRR-CT-901-2013-01	Version: 1.0	01AUG2014
© Confidential IrriMax Corporation		Page 34 of 35

Study Number IRR-CT-901-2013-01	Version: 1.0	01AUG2014
© Confidential IrriMax Corporation		Page 35 of 35

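### The supportive SSI model picks covariates by between-arm significance tests, names no centre term and does not clearly exclude variables recorded after randomisation (minor)

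*Combined protocol and SAP*

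**What the plan says.** Under Efficacy Analyses, Primary Endpoint, the protocol expects the arms to be balanced and plans a supportive logistic regression in case they are not. The model holds treatment plus key baseline or demographic variables that turn out imbalanced. The selection rule is: "Identification of variables to include will be based on comparisons between the two groups using appropriate two-sided tests", and then "Those variables that are found to be significant (p < 0.05) will be included in the model". The output is an adjusted odds ratio with a 95% confidence interval. No centre term is named.

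Four other places bear on this:

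- **Centre.** The Randomization section stratifies by centre, and the primary Cochran-Mantel-Haenszel (CMH) test is stratified by site.
- **Baseline comparisons.** Demographics and Baseline Summaries states: "The comparability of the treatment groups for relevant demographic and baseline characteristics will be assessed by descriptive statistics". The next sentence is: "No statistical hypothesis tests will be performed".
- **Intra-operative variables.** The same section lists among the baseline characteristics "primary injury in trauma or primary organ(s) in the acute abdomen and intraoperative risk factors". The Protocol Synopsis names examples, beginning "Intra-operative SSI risk factors including drains, staple versus sutures, surgical time (skin to skin", and says that these factors "are assessed and risk adjusted in the final analysis", without naming the model.
- **Exploratory model.** Exploratory Analyses plans a separate stepwise SSI model with hospital dummy variables.

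Statistical Methods promises a separate, more detailed SAP before the first patient is enrolled. It is not among the documents reviewed.

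**The concern.** A supportive adjusted analysis should show whether the treatment estimate holds once known predictors of SSI are taken into account. Selecting covariates by a between-arm test does not do that. A strong predictor that happens to be balanced is left out, and an irrelevant variable that happens to differ is put in. The set of covariates is then known only after the data are in, and it would differ if the trial were repeated. Leaving out centre also makes the supportive model match the design less closely than the primary test does.

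Eligibility raises a second question. Randomisation takes place in the operating room (Randomization; the visit schedule lists it before surgery), so drains, closure type, operating time, transfusion and body temperature during surgery are largely recorded afterwards, in an open-label trial. Adjusting for something the assigned arm may have influenced can distort the treatment estimate. The text should say whether such variables can enter this model.

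At stake is how the supportive odds ratio is read, not whether the trial succeeds.

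**Working it through.** **1. The plan's own figure.** With 300 per arm, 20% v 10% SSI and a two-sided 5% chi-square test (Power and Sample Size), power recomputes to 93.1%, against 93% in Table 2.1. The other eight cells also reproduce. Nothing below changes them, because the supportive model plays no part in the sample size or the success rule.

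**2. How many covariates the rule admits.** Under randomisation each pre-randomisation candidate has about a 5% chance of p < 0.05, whether or not it predicts SSI. The plan does not define which variables are key, so the number n is an assumption and a range is shown. Independence is also assumed. Expected entries = 0.05n; P(none enters) = 0.95^n.

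| n | Expected entries | P(none enters) |
|---|---|---|
| 12 | 0.6 | 0.540 |
| 20 | 1.0 | 0.358 |
| 32 | 1.6 | 0.194 |

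The chance that at least one of four true predictors enters is 1 − 0.95^4 = 18.5%. A simulation with 25 candidates, four of them prognostic, gave the same picture: something was selected in 73% of runs, but a prognostic variable in only 19%.

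**3. What the rule leaves unadjusted.** Take a binary factor with 30% prevalence (assumed). The largest arm difference that stays non-significant is 1.96 × sqrt(0.3 × 0.7 × 2/300) = 0.073, or 7.3 points. With overall SSI at 20% and no treatment effect, a difference of that size alone multiplies the treatment odds ratio by 1.023, 1.056 or 1.091 if the factor's odds ratio for SSI is 1.35, 2 or 3 (assumed). This is the extreme of what can be missed. The median imbalance among unselected variables is about 2.4 points, and the shifts are then about 0.7%, 1.8% and 2.9%.

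**4. How far the resulting estimate moves.** The simulation used 600 patients in 13 centres, 1:1 within centre, control SSI of 20%, four binary predictors (30% prevalence) plus 16 noise variables, and a centre SD of 0 or 0.5 on the log-odds scale, with 2,000 replicates per setting. Predictor odds ratios were assumed to be weak (1.2 to 1.5), middle (1.8 to 2.5) or strong (3 each). The selected-covariate odds ratio fell within 5% of the unadjusted one in 79% to 94% of trials. Under the null the rule rejected in 3.5% to 5.0% of trials (Monte Carlo SE about 0.5 points), so it does not inflate type I error.

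**5. What a fixed list does to the estimate.** At 20% v 10% without centre variation, the median odds ratio from a fixed list (fitted conditionally on site) was 0.441, 0.417 or 0.388 for weak, middle or strong predictors. The unadjusted medians were 0.446, 0.440 and 0.442. The fixed list therefore changes the reported estimate, and more so when predictors are strong.

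**The case against.** The strongest reply is that little depends on this model. It is labelled supportive, and success rests on the site-stratified CMH test, which already gives an adjusted relative risk. The exploratory SSI model has hospital dummies, so centre is not ignored overall. All of that stands, and it is why the point is minor. It does not justify a selection rule driven by chance.

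Four stronger readings are tempting, and the documents do not support them.

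- **A flat contradiction.** A reader might say that the selection tests and the baseline section cannot both hold. But the ban on tests sits under the baseline summaries and may be meant only for those tables. What remains is unclear scope.
- **Intra-operative variables will enter.** No passage says so. The supportive model is limited to key baseline and demographic variables, and the exploratory model could satisfy the synopsis statement on risk adjustment. What remains is that the baseline section lists these factors as baseline, so they are not clearly kept out.
- **Operating time is lengthened by the study arm.** The instructions for use say "Allow solution to dwell for one (1) minute" and apply this twice. But standard care may also include irrigation at the investigator's discretion, and that takes time too. The net difference between arms is not documented.
- **Power is lost.** Any gain from a fixed list depends on prognostic strength that the documents do not give, and with weak predictors it is close to nil. The plan asks this model only for odds ratios and intervals, so power is not the basis of the point.

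The unseen SAP may define the key variables. The entry rule would still stand in the protocol.

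**Conclusion.** The point holds, at minor severity. The supportive model selects covariates by chance imbalance rather than prognostic value and names no centre term despite the stratified design. The text does not clearly exclude variables recorded after randomisation, and the rule sits awkwardly beside the descriptive-only baseline section. In practice the adjusted odds ratio will usually repeat the unadjusted one and so offers little support.

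The entry rates rest on an assumed number of independent candidates. The odds-ratio shifts and simulation results rest on assumed prevalence, predictor strength and centre variation. That the rule selects without regard to prognosis needs none of these assumptions; it follows from randomisation.

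**What to change.** Replace the two selection sentences with wording such as: *The supportive analysis will be a logistic regression with treatment, a random centre effect and a short list of pre-randomisation factors, fixed before any outcome data are seen and fitted regardless of observed balance. Variables recorded after randomisation are not eligible.* Choose one method for centre; a random effect keeps sites with no SSI, which a fit conditional on site would drop.

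Put the list in the protocol or in the promised SAP. Factors already collected would serve, for example trauma v acute abdomen, ASA class, diabetes and shock on admission. That is an illustration, because the documents do not rank predictors. State whether the same model applies to readmission, which is analysed by the same methods.

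In Demographics and Baseline Summaries, report intra-operative factors separately from baseline. Amend the Protocol Synopsis so that they are adjusted for only in the exploratory model.

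**Cost.** No new data are needed, but this changes the fitted model, not only the wording. The odds ratio becomes more conditional, typically further from 1 than the unadjusted one when predictors are strong, and the report must say so. At 20% v 10% there are about 300 × 0.20 + 300 × 0.10 = 90 events. Treatment plus four factors (one term each) gives 90/5 = 18 per term, before the centre variance. If the study has begun, Statistical Methods may require an amendment or a listing in the clinical study report, depending on how this analysis is classed.

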- Recorded data from automated instruments such as (ECGs, rhythm strips, electroencephalograms (EEGs), pulmonary function tests, etc.)
- Records of telephone contacts
- Evaluations checklists
- Study Product distribution and accountability logs maintained by study personnel
- Correspondence between physicians or memoranda to IRBs/IECs regarding any subject's treatment

Statistical Methodology:

Endpoints

Efficacy

Primary

The primary efficacy endpoint is the rate of SSI observed within 30 days from the date of index operation.

Secondary

The secondary efficacy endpoints will include the following:

- The length of stay in the hospital
- Rate of readmission to the hospital, within 30 days from the date of the index operation
- Estimated costs of the index hospitalization

Exploratory Endpoints

The following outcomes will be reviewed as exploratory endpoints:

- Superficial surgical site infection (SSI)
- Deep surgical site infection (SSI)
- Organ/space surgical site infection (SSI)
- Ventilator associated pneumonia (VAP)
- Catheter associated urinary tract infection (CAUTI)
- Central line associated blood stream infection (CLABSI)
- Deep vein thrombosis (DVT)
- Pulmonary embolus (PE)
- Acute cardiac event

Study Number IRR-CT-901-2013-01	Version: 1.0	01AUG2014
© Confidential IrriMax Corporation		Page 27 of 35

- Clostridium difficile (C-diff) infection
- MRSA infection
- Mortality

Safety

The safety of the IrriSept irrigation unit will be assessed through the clinical review and analysis of adverse events.

Randomization

Subjects who meet all inclusion and exclusion criteria will be centrally randomized in the OR in a 1:1 ratio to either the study product group or the control group, in accordance with a computer-generated block randomization schedule prepared by a non-study statistician. A unique randomization number and associated treatment assignment will be made using an interactive web-based response system (IWRS). Randomization will be stratified by center with no center allowed to enroll more than 120 subjects.

Statistical Methods

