This section outlines the statistical analysis strategy and procedures for the study. If, after the study has begun, changes are made to primary and/or key secondary hypotheses, or the statistical methods related to those hypotheses, then the protocol will be amended (consistent with ICH Guideline E-9). Changes to exploratory or other non-confirmatory analyses made after the protocol has been finalized, along with an explanation as to when and why they occurred, will be listed in the Clinical Study Report (CSR) for the study. Post hoc exploratory analyses will be clearly identified in the CSR. A separate Statistical Analysis Plan (SAP) with further details than presented here will be finalized prior to first patient enrolled to minimize any bias, as the study is non-blinded.

Power and Sample Size

The determination of sample size for this study is based on the primary objective to demonstrate the superiority of the IrriSept irrigation unit versus conventional standard of care in patients who undergo open abdominal laparotomy for abdominal trauma or acute surgical abdomen within 36 hours of initial presentation to their healthcare organization. The primary endpoint is the rate of SSI observed within 30 days (+/- 3 days) from the date of the index operation.

Based on historical data, it is assumed that the rate of SSI within the standard of care group will be \geq 20%. A total of 600 patients (300 per group) will provide \geq 90% power to demonstrate a reduction in the rate of SSI, up to 50%, assuming a control group rate for SSI of \geq 20%, based on a two-sided Chi-square test with a 5% significance level. The following table shows the power achieved under various combinations of control group SSI rates and relative treatment differences.

Table 2.1: Power associated with a total sample size of 600 (n=300/group), based on a two-sided Chi-square test with a 5% significance level.

Control Group SSI	Relative Treatment Difference (IrriSept/Control)		
Rate	50% Reduction	40% Reduction	30% Reduction
15%	83%	62%	38%
20%	93%	76%	50%
25%	98%	87%	61%

It is anticipated that approximately 1100 patients will be screened, 650 patients will be enrolled, to obtain 600 evaluable patients, based on a non-evaluable rate of approximately 5%. All calculations were carried out in SAS version 9.2 using the comparison for two independent proportions procedure in PROC POWER.

Study Number IRR-CT-901-2013-01	Version: 1.0	01AUG2014

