© Confidential IrriMax Corporation		Page 28 of 35

Analysis Populations

Intention-to Treat (ITT)

The intention-to-treat population will be defined as all randomized subjects. Subjects will be assigned to a group based on the group they were randomized to.

Per-Protocol Population (PP)

Within the ITT population, subjects will be considered evaluable if they completed the 30 day follow up visit. Subjects who are withdrawn from the study prior to the 30 day follow up will be designated "non-evaluable" and excluded from the PP population.

Safety Analysis Set (SAS)

The safety analysis set will consist of all randomized subjects who underwent an emergency operation. The safety analysis set will be used for all safety analyses. Subjects will be assigned to a group based on the actual procedure received.

Efficacy Analyses

Primary Endpoint

For the primary endpoint, the number and proportion of patients with a SSI observed within 30 days from the date of emergency operation will be summarized by treatment group, along with the difference and 95% confidence interval for the difference (based on the Wald method). If a patient is missing their end of study assessment, or if they died prior to the end of study assessment, they will be classified as having met the primary endpoint of a SSI. A comparison between treatment groups will be made using the Cochran-Mantel-Haenszal test, stratified by site. The two-sided p-value, the adjusted relative risk (IrriSept/Control) and 95% confidence interval of the relative risk (based on the Wald method) will be reported. The study will be deemed successful if the two-sided p-value for the end of study treatment difference is < 5%.

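### Length of stay: the estimate and CI come from a mixed model with a random centre effect, but the p-value beside them is from a two-sample t-test that, as named, ignores centre

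*Combined protocol and SAP*

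**What the plan says.** All references are to the statistical section of the protocol.

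- **Secondary Endpoints, length of stay, model.** The plan states that "a comparison of the LOS between the two treatment groups will be made by modeling the log LOS using a mixed effect model". The terms of that model are then given: it is to be fitted "with a fixed effect term for treatment and a random component for center". The plan's reason for the log scale is the skewness of LOS.
- **Secondary Endpoints, length of stay, reporting.** The next sentence says the means and 95% CIs for the treatment difference "will be back transformed and presented along with the two-sided p-value from a two-sample t-test". It does not say on which scale the t-test is run, whether centre enters it, or whether the model's own treatment test is meant.
- **Randomization.** "Randomization will be stratified by center with no center allowed to enroll more than 120 subjects".
- **Primary Endpoint.** The comparison of SSI rates "will be made using the Cochran-Mantel-Haenszal test, stratified by site".
- **Secondary Endpoints, readmission.** This endpoint "will be analyzed using the same methods as described for the primary endpoint", so its p-value is also stratified by site.
- **Statistical Methods.** "A separate Statistical Analysis Plan (SAP) with further details than presented here will be finalized prior to first patient enrolled". No such separate plan is among the documents supplied, so this point is limited to the protocol text.

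**The concern.** Read literally, the plan reports one result from two procedures: the effect and interval from a centre-adjusted model, and the p-value from an unadjusted test. A p-value and a 95% CI shown together are normally expected to agree on whether no difference is excluded. Here they need not.

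The direction is predictable. Randomisation is 1:1 within centre, so centre differences contribute almost nothing to the error of the treatment contrast. They do stay in the t-test's residual variance, so its standard error is too large. The t-test is therefore the more conservative of the two. The typical conflict would be a CI excluding no difference beside p > 0.05, and the plan has no rule for which of them governs. In an open-label trial that choice should not be left until the data are in.

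The natural reading is a t-test on log LOS. The text does not exclude a test on raw days, but that would go against its own reason for taking logs, and nothing below depends on it.

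**Working it through.** The plan gives no SD, effect, power or between-centre variance for LOS, so there is no figure of its own to reproduce.

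**Inputs from the protocol.** 600 patients, 300 per group (Power and Sample Size); 12 to 14 centres, 13 used here (Protocol Synopsis); at most 120 per centre, 1:1 blocked allocation stratified by centre (Randomization). The two-sided 5% level is stated for the primary endpoint and is assumed here for LOS.

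**Assumptions.** Intraclass correlation (ICC, the between-centre share of log LOS variance) from 0 to 0.20. Effect d = difference in mean log LOS divided by the total log SD, so no separate SD is needed. Block size 4, normal centre effects and residuals, unequal centre sizes.

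**Step 1. Large-sample relation.** With equal allocation within centre and total log variance set to 1:

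- SE of the mixed-model contrast ≈ √(4(1 − ICC)/600)
- SE of the t-test ≈ √(4/600)
- so the t statistic ≈ √(1 − ICC) × the model statistic.

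The two conflict when the model statistic lies between 1.96 and 1.96/√(1 − ICC).

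| ICC | SE ratio 1/√(1 − ICC) | Upper limit 1.96/√(1 − ICC) | Model p-values in conflict |
|---|---|---|---|
| 0.05 | 1.03 | 2.011 | 0.044 to 0.05 |
| 0.10 | 1.05 | 2.066 | 0.039 to 0.05 |
| 0.20 | 1.12 | 2.191 | 0.028 to 0.05 |

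**Step 2. Worst case over d.** The chance of landing in that strip is greatest when the expected model statistic, d × √150/√(1 − ICC), sits at its middle. It is then about the strip's width times the peak normal density, 0.399. At ICC 0.10: (2.066 − 1.960) × 0.399 = 0.042. The same calculation gives 0.8%, 2.0%, 4.2% and 9.2% at ICC 0.02, 0.05, 0.10 and 0.20, at d of about 0.15 to 0.16.

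**Step 3. Simulation.** 10,000 trials per setting; REML random-intercept model with a Wald t-test on 586 degrees of freedom, against a pooled two-sample t-test on log LOS. Percentage of trials in which the CI excludes no difference but the t-test gives p > 0.05:

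| d | ICC 0 | 0.02 | 0.05 | 0.10 | 0.20 |
|---|---|---|---|---|---|
| 0.16 | 0.2 | 0.7 | 1.8 | 3.7 | 8.2 |
| 0.20 | 0.1 | 0.6 | 1.6 | 3.1 | 6.9 |
| 0.25 | 0.0 | 0.4 | 0.9 | 2.0 | 3.7 |

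Rejection rates under no effect (%):

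| Test | ICC 0 | 0.02 | 0.05 | 0.10 | 0.20 |
|---|---|---|---|---|---|
| t-test | 4.7 | 4.9 | 4.6 | 3.8 | 3.0 |
| Mixed model | 4.8 | 5.0 | 5.0 | 4.9 | 5.1 |

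Power at d = 0.20, mixed model against t-test: 70.7% v 69.1% (ICC 0.05), 73.4% v 70.3% (0.10), 78.0% v 71.1% (0.20). Monte Carlo error is at most about 0.3 points on the conflict rates and about 0.2 points on the null rates. The row for d = 0.16 is near the worst case, with power of about 50 to 59%.

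**Step 4. Reverse conflict and sensitivity.** A significant t-test beside a CI that includes no difference occurred in at most 2 of 10,000 trials when all randomised patients are analysed. If 650 are enrolled and 50 (7.7%) are lost at random, the balance within centre is less exact and the reverse rises to about 0.05 to 0.3%. Rounding LOS to whole days (assumed geometric mean 7 days, log SD 0.8), or analysing 650 patients, leaves the main conflict at d = 0.20 at 1.3 to 1.5%, 3.4 to 3.5% and 6.3 to 7.1% for ICC 0.05, 0.10 and 0.20.

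**The case against.** The strongest reply is that this is only loose wording. The preceding sentence says the comparison is made by the mixed model, and the test of a two-level treatment term in that model is itself a t-test. On that reading the p-value and CI already agree. This is possible, and the text does not settle it. But the model's treatment test is not a two-sample t-test, and a programmer following the sentence literally would run the other procedure. The same edit serves both readings.

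Second, the promised separate analysis plan may settle the matter. It may, but it was not available, and further detail there would not by itself remove a conflicting instruction in the protocol.

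Third, the primary endpoint is an imperfect standard. Its risk difference has a Wald interval, with no stratification stated, beside a site-stratified p-value, and the supportive logistic regression and the subgroup models list no centre term. That stands: the plan does not adjust for centre consistently. It does not make the LOS pairing coherent.

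Fourth, the effect is small and its size rests on an assumed ICC. That also stands. At ICC 0.05 or below, no simulated conflict rate exceeds 1.8%, and the larger figures need an ICC that the documents neither support nor exclude.

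**Conclusion.** The point holds, as a minor one. As written, the LOS p-value comes from a different procedure than the estimate and CI, and that procedure leaves out the factor by which randomisation is stratified. Nothing in the supplied text reconciles them.

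On the log scale the consequence runs almost entirely one way: a conservative p-value beside a correct CI. It is negligible if LOS varies little between centres and grows with the between-centre share of variance. Everything numerical rests on the assumed ICC and d, and on the literal reading of the sentence.

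The matter is confined to the reporting of one secondary endpoint. The SSI test and the success criterion are unaffected, and the Multiplicity section plans no adjustment among secondary endpoints that this p-value could disturb.

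**What to change.** In the length-of-stay paragraph of Secondary Endpoints, replace the reference to a two-sample t-test with the two-sided p-value for the treatment term of the same mixed model on log LOS, using the same degrees of freedom as the CI. The p-value and CI then agree by construction. If the separate analysis plan already says this, bring the protocol into line with it. For clarity only, describe the back-transformed contrast as a ratio of geometric means.

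The cost is one clause, with no new data and no new analysis. The Statistical Methods section has a rule for edits made once the trial is running: where "changes are made to primary and/or key secondary hypotheses, or the statistical methods related to those hypotheses, then the protocol will be amended". So if enrolment has started and LOS counts as a key secondary hypothesis, the edit has to be made as a protocol amendment.
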